8.2. Operational Definitions for (S)AEs

The following circumstances are not considered SAEs:

- Routine treatment or monitoring of the studied indication not associated with any deterioration in condition.
- Treatment which was elective or pre-planned, for a pre-existing condition not associated with any deterioration in condition.
- Any admission to hospital or other institution for general care where there was no deterioration in condition.

- Treatment on an emergency, outpatient basis for an event **not** fulfilling any of the definitions of serious as given above and not resulting in hospital admission.

As a low-risk study, any AE occurring will be recorded within the CRF and participant's medical records. The study is comparing two approaches to impression taking which are used routinely within the orthodontic department, therefore the perceived study risks are no greater than that normally faced by orthodontic patients. The study is unlikely to encounter any significant adverse events and therefore will not be reporting these.

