8.3. Recording and Reporting SAEs

All AEs and SAEs must be recorded from the time of randomisation until 4 weeks after the last visit.

All SAEs occurring during the duration of the study must be recorded by the investigator within the CRF. The PI is responsible for checking for SAEs when participants attend for treatment and follow-up.

All related and unexpected SAEs must be reported by the investigator using the 'non-CTIMP safety report to REC form' from the HRA website. The completed form should be submitted to the Sponsor and REC within 15 days of the CI becoming aware of the event. Safety information will be reviewed during trial management group meetings.

UHDB contact information:

Email: [contact]

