[E.7] Statistical Methods for Sensitivity Analyses [Protocol Sec. 10.3.2]

[E.7.1] If there are missing data in the primary endpoint, the plausibility that outcome data are missing at random (MAR) from the primary endpoint will be examined, and if it doesn't hold, sensitivity analysis will be conducted. Otherwise, sensitivity analyses will not be undertaken.

[E.8] Definition of Safety Endpoints [Protocol Sec. 8]

[E.8.1] The safety endpoints will be the reported SAEs and SUSARs.

[E.9] Statistical Methods for Safety Endpoints

[E.9.1] The number and percentage of patients reporting a SAE or SUSAR will be summarised by treatment group and compared using a Chi-Square test.

[F] Analysis Groups and Missing Data

[F.1] Definition of Analysis Groups [Protocol Sec. 10.7]

[F.1.1] **Modified Per Protocol:** All participants who were randomised and experienced at least one of the study treatments will be included in the primary analysis. Participants will be

analysed according to the treatment sequence they received, if this differs from the treatment sequence to which they were allocated.

The safety data will be reported for all participants who experienced at least one of the study treatments. They will be reported according to the treatment they received at the time of experiencing the SAE or SUSAR, or the most recent treatment if the event occurred after the method was administered.

[F.1.2] Per protocol: If required, the secondary analysis will be carried out on patients who experienced both procedures. They will be analysed according to the treatment sequence they received if this differs from the treatment sequence to which they were allocated.

[F.2] Definition of Inclusion Groups

[F.2.1] Complete Dataset Population: Missing data are expected to be small and the primary analysis is planned to be carried out on a complete case basis. For the secondary analyses, any participant who has incomplete data will be excluded from the analysis that requires those data.

[F.3] Procedure for Accounting for Missing, Unused, and Spurious Data [Protocol Sec. 10.8]

[F.3.1] If there are missing data in the primary endpoint, then multiple imputation using chained equations will be applied. Missing data will not be imputed for any of the secondary endpoints, which will be analysed on a complete case basis.

[G] Comments

[G.1.1] The analyses will be carried out using STATA.

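### SAP E.9.1 plans a chi-square test on SAE and SUSAR counts that are likely to be too sparse for it, in a crossover where completers sit in both columns, while the AEs that the protocol has recorded and graded get no planned summary by procedure

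*SAP*

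**What the plan says.** SAP E.8.1 defines safety narrowly: "The safety endpoints will be the reported SAEs and SUSARs". SAP E.9.1 has the number and percentage of patients with such an event "summarised by treatment group and compared using a Chi-Square test". It gives no significance level, no rule for sparse or zero counts, and no statement on continuity correction.

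SAP F.1.1 sets the population and the attribution rule: "The safety data will be reported for all participants who experienced at least one of the study treatments", and "They will be reported according to the treatment they received at the time of experiencing the SAE or SUSAR", or to the most recent procedure if the event came afterwards.

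On collection, protocol 8.2 says that "any AE occurring will be recorded within the CRF" and protocol 8.3 that "All AEs and SAEs must be recorded from the time of randomisation until 4 weeks after the last visit". Protocol 8.3.1 asks for severity and causality of AEs, and the CRF contents in protocol 9.1 include an adverse event form.

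On reporting, protocol 8.2 ends: "The study is unlikely to encounter any significant adverse events and therefore will not be reporting these". Protocol 8.3 then states: "All related and unexpected SAEs must be reported by the investigator", to the Sponsor and REC within 15 days.

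**The concern.** Two things do not fit together. First, the test in E.9.1 is an independent-groups, large-sample test. It is to be applied to events that the protocol expects to be rare, in a design where the same people contribute to both columns. The p-value would then be either unavailable or based on an approximation that does not hold, and a non-significant result could be read as reassurance about safety that the data cannot give.

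Second, investigators are asked to record every AE and judge its severity and cause, but the SAP text plans no table of this information. A non-serious related event, such as a mild reaction to alginate (a risk named in protocol 12.1), would be on the CRF without a defined place in the analysis by procedure.

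The closing sentence of protocol 8.2 adds uncertainty about which events are to be reported at all.

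**Working it through.** **Denominator.** The plan has no safety calculation to reproduce, so its only relevant figure is the sample size (protocol 10.1: SD 29.85, difference 11 mm, two-sided 0.05, power 0.90, 7% dropout). Taking 29.85 as the SD of the within-participant difference, N = ((1.960 + 1.282) × 29.85 / 11)² = 77.4, rounded up to 78, or 39 per sequence. Then 39 / 0.93 = 41.9, so 42 per sequence and 84 in total, as stated. In the crossover each procedure therefore has at most 84 participants.

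**Expected counts.** Let k be the number of participant-events (a participant counted once under a procedure), summed over two columns of 84. Under no difference, the expected count in each event cell is k/2. For this to reach 5, k must be at least 10, that is 10/168 = 6.0%.

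**Small tables.** For k/84 v 0/84, Pearson's statistic is 168k / (168 − k). For k = 4 this is 672/164 = 4.10. With Yates' correction it is 168 × (336 − 84)² / (84 × 84 × 4 × 164) = 2.30. If the four events are in four different people who had both procedures, exact McNemar gives 2 × 0.5⁴ = 0.125.

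| Split | Smallest expected | Pearson p | Yates p | Fisher p | Exact McNemar p |
|---|---|---|---|---|---|
| 0 v 0 | 0 | not computable | not computable | – | – |
| 1 v 0 | 0.5 | 0.316 | 1.0 | 1.0 | 1.0 |
| 4 v 0 | 2.0 | 0.043 | 0.129 | 0.121 | 0.125 |
| 5 v 0 | 2.5 | 0.023 | 0.069 | 0.059 | 0.063 |

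Asymptotic McNemar at 4 v 0 is 0.046, close to Pearson, so small counts rather than pairing cause the gap. With 78 per column the 4 v 0 values are 0.043 (Pearson), 0.129 (Yates) and 0.120 (Fisher).

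**How often this arises.** The documents give no SAE rate, so the risks below are assumptions. The two columns are treated as independent Binomial(84, p), which gives P(no event) = (1 − p)¹⁶⁸ and P(expected count at least 5) = P(Binomial(168, p) ≥ 10). The last columns enumerate all tables when the two procedures have equal risk.

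| Assumed risk per procedure | No event, no test | Expected count ≥ 5 | Pearson p < 0.05 | Yates p < 0.05 |
|---|---|---|---|---|
| 0.1% | 85% | < 0.001% | 0.0003% | < 0.0001% |
| 0.5% | 43% | < 0.001% | 0.12% | 0.0006% |
| 1% | 18% | 0.0009% | 0.88% | 0.02% |
| 2% | 3% | 0.22% | 3.3% | 0.27% |
| 5% | 0.02% | 33% | 4.2% | 1.6% |

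**Pairing.** With a within-person correlation of 0.3, so that P(event under both) = p² + 0.3p(1 − p), the uncorrected Pearson rejection rate falls to about 0.3% at 1% risk, 1.8% at 5% and 2.0% at 10%; with independent columns the last is 5.0%. The chance of no event at 0.1%, 0.5% and 1% becomes 87%, 49% and 24%. Ignoring the pairing is therefore conservative if the correlation is not negative.

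**AE coverage.** Outside E.8 and E.9, the only traces of safety output are the template tables in SAP Appendix A. They cite D.9.1 to D.9.3, although section D of the SAP concerns interim analysis. One row gives adverse reaction diagnoses for the whole study population; it is limited to reactions, is not split by procedure and has no severity. Two more rows give the numbers of SARs and SAEs by treatment as a mean or median, whereas E.9.1 asks for the number and percentage of patients. None gives AEs by procedure.

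**The case against.** The strongest reply is that nothing turns on this test. E.9.1 sets no significance level, protocol 10.3.2 holds only the primary analysis to one, and safety is not among the objectives or outcomes in protocol section 3. With no events, the number and percentage would still be reported; only the p-value would be lost. The choice between Pearson and Yates changes the verdict at 0.05 in only 0.0003%, 0.11% and 0.86% of null trials at risks of 0.1%, 0.5% and 1%. All of this stands, and it keeps the point minor.

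A reader might infer from the 4 v 0 example that the test will produce false safety signals. The enumeration does not support that: at these risks the test rejects far less often than 5%. The limit on this statement is negative within-person correlation. If no one could have an event under both procedures, the rejection rate at 10% risk would be 6.2%, but nothing in the documents suggests such a pattern.

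A reader might also infer that protocol 8.2 forbids what 8.3 requires. That is not shown. The sentence can mean that AEs are recorded but not reported onward, with 8.3 adding a specific duty for related and unexpected SAEs. A contradiction arises only if the undefined word for the events in 8.2 includes serious ones. What can be said is that the sentence is ambiguous.

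Finally, the foreseeable discomforts (pain, nausea or coughing, sickness) are compared by procedure as VAS outcomes under SAP E.5.1, and protocol 8.3 has the trial management group review safety information. Both are true. VAS scores are not AE counts, however, and oversight meetings are not a planned tabulation.

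**Conclusion.** The point holds and is minor. The chi-square test in E.9.1 does not suit the data it is planned for: the columns share participants, and at assumed risks up to 2% per procedure an adequate expected count is reached in under 0.3% of trials. The p-value will be uncomputable or unreliable. Usually it will be conservative, with null rejection below 1% at risks up to 1% if within-person correlation is not negative, so a non-significant result is close to guaranteed and uninformative.

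Separately, AEs are recorded and graded under the protocol but have no planned summary by procedure in the SAP, and the Appendix A templates neither supply one nor match E.9.1.

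The figures rest on assumed rates, on at most 84 participants per procedure, and on independent columns except where stated. The primary analysis and the VAS and time analyses are not affected.

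**What to change.** In SAP E.9.1, delete the chi-square test. In SAP E.8.1, add AEs. Report descriptively, by the procedure received or most recent (the F.1.1 rule extended to AEs), the number and percentage of participants with any AE and with any SAE, and the number of events, by severity and relatedness. The denominator is the participants who received that procedure. Make the Appendix A safety tables match and correct their section references.

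If a p-value is kept, use exact McNemar in participants who had both procedures, and state that it leaves out those who had only one and ignores period effects.

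Reconcile the last sentence of protocol 8.2 with 8.3 and with SAP E.8 and E.9, so that it is clear which events it refers to and what kind of reporting is meant.

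The cost is some SAP wording, one descriptive table from data already on the CRF, and one clarified protocol sentence. Design, data collection and the primary analysis do not change.

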In addition, two secondary analyses of the primary outcome may be undertaken. The first analysis will be conducted and will use a two-period two-treatment mixed effects model: Participant effects will be treated as random and a treatment-by-period interaction (for this analysis, this is the carryover effect) will be included in the model. If some participants have not complied with the protocol, a second analysis of the primary outcome will be conducted just including participants that were compliant (i.e.

a per protocol analysis). For both of these analyses, the mean effects will be reported, with 95% confidence intervals.

Only the primary analysis will be compared against a specific level of significance. The secondary analyses should be considered as hypothesis generating rather than providing firm conclusions.

The analysis will be undertaken by the study statistician. The study statistician will draft the Statistical Analysis Plan (SAP) according to CTU-SOP-019 (Statistical Analysis Plan), which will be reviewed by the CI and approved by the CI and the study statistician. The analysis will be carried out using STATA® and a statistical report produced.

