10.7. Analysis Groups

All participants who were randomised and experienced at least one of the study treatments will be included in the primary analysis. Participants will be analysed according the treatment sequence they received, if this differs from the treatment sequence to which they were allocated.

The potential re-analysis of the primary analysis will be carried out on a per protocol basis (i.e. only participants without major protocol deviations who completed the study with the treatment that was originally allocated will be included).

All participants who completed the study will be included in the other secondary analyses. Participants will be analysed according the treatment sequence they received, if this differs from the treatment sequence to which they were allocated.

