[E.4.5] The time taken to make the impression or complete the scan will be recorded (mins)

[E.4.6] A secondary analysis of the primary outcome will be undertaken using a two-period two-treatment mixed effects model.

[E.4.7] If some participants have not complied with the protocol, a second analysis of the primary outcome will be conducted just including participants that were compliant.

[E.5] Statistical Methods for Secondary Analyses [Protocol Sec. 10.3.2]

[E.5.1] Eight of the secondary outcomes will be recoded using VAS scores (see Sections E.4.2 and E.4.4). The differences between the paired VAS scores of these secondary outcomes will be reported using means and 95% confidence intervals. They will be compared using analysis of variance (ANOVA) that will analyse the period, treatment and sequence effects of the comfort scores. Analysis of the secondary endpoint will be assessed using 2-sided tests with a significance level of 0.05.

[E.5.2] The mean difference in the time required for each procedure (Section E.4.5) will be reported, with 95% confidence intervals. The difference in time will be compared using analysis of variance (ANOVA) that will analyse the period, treatment and sequence effects of the comfort scores. Analysis of the secondary endpoint will be assessed using 2-sided tests with a significance level of 0.05.

[E.5.3] The operator's preference for each impression (Section E.4.6) will be tabulated and reported using frequencies and percentages.

[E.5.4] The secondary analysis of the primary outcome using a two-period two-treatment mixed effects model (Section E.4.7) will be undertaken with participant effects treated as random and a treatment-by-period interaction (for this analysis, the carryover effect) included in the model. The mean effects will be reported, with 95% confidence intervals.

[E.5.5] The potential second analysis of the primary outcome (Section E.4.8) will be a per protocol analysis of the difference between the paired VAS. This will be carried out using an analysis of variance (ANOVA) that will analyse the period, treatment and sequence effects of the comfort scores. Analysis of the primary endpoint will be assessed using 2-sided tests with a significance level of 0.05. The mean effects of this model will be reported, with 95% confidence interval

[E.6] Statistical Methods for Sub-group Analyses [Protocol Sec. 10.4]

[E.6.1] There will be no sub-group analyses

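### SAP F.1.2 defines the per-protocol set as everyone who had both procedures, with no compliance test, contrary to Protocol 10.7 and to SAP E.4.7

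*SAP*

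**What the plan says.** Four places in the two documents describe who enters the per-protocol re-analysis of the primary outcome.

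- **SAP F.1.2**, headed as the per-protocol group: "If required, the secondary analysis will be carried out on patients who experienced both procedures". It adds: "They will be analysed according to the treatment sequence they received if this differs from the treatment sequence to which they were allocated".
- **Protocol 10.7**, second paragraph: "only participants without major protocol deviations who completed the study with the treatment that was originally allocated will be included".
- **Protocol 10.3.2**: if there has been non-compliance, "a second analysis of the primary outcome will be conducted just including participants that were compliant".
- **SAP E.4.7** sets the same restriction: "If some participants have not complied with the protocol, a second analysis of the primary outcome will be conducted just including participants that were compliant". SAP E.5.5 calls this analysis per protocol and attaches a two-sided 0.05 test to it.

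The third paragraph of Protocol 10.7 has a separate rule for different analyses: "All participants who completed the study will be included in the other secondary analyses". Those participants are analysed by the sequence they received.

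**The concern.** F.1.2 omits both conditions that make the protocol's set a per-protocol set: absence of major deviations and completion as allocated. Its second sentence goes further and expressly keeps people whose sequence departed from allocation. Its content matches the completers rule that Protocol 10.7 reserves for the other secondary analyses, so the wrong paragraph may have been carried across. F.1 cites Protocol 10.7 as its source, and the SAP's comments section announces no change from it.

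At stake is the only planned check on deviations. SAP E.7.1 rules out sensitivity analyses except where the missing-at-random assumption fails. Completers with a wrong order, an eligibility breach or an interval below the protocol's 4-week minimum would stay in both the primary and the per-protocol analysis. The protocol itself regards two of these as possible sources of bias: recent experience of a scan or impression (12.1) and too short a gap between visits (7.6).

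Two gaps remain even if Protocol 10.7 is followed. Neither document defines a major deviation or compliance. And Protocol 10.7 speaks of the treatment allocated, while Protocol 7.3 allocates only the order, so the status of a wrong-order completer is not explicit.

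**Working it through.** **Step 1. The rules side by side.**

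| Participant | SAP F.1.2 | Protocol 10.7, per protocol | Protocol 10.3.2 and SAP E.4.7 |
|---|---|---|---|
| Had one procedure only | out | out | not stated; compliance undefined |
| Both procedures, order opposite to allocation | in, by order received | out on the natural reading | not stated; compliance undefined |
| Both procedures, eligibility breach | in | out if major | not stated; compliance undefined |
| Both procedures, interval under 4 weeks | in | out if major | not stated; compliance undefined |
| Both procedures, no deviation | in | in | in |

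The rows where F.1.2 and Protocol 10.7 can differ are those of completers who deviated.

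**Step 2. Overlap with the primary set.** SAP F.1.1 takes everyone randomised who had at least one procedure, by sequence received. The endpoint is a paired difference and needs both comfort scores. Under the complete-case rule in SAP F.2.1, the primary analysis therefore uses essentially the F.1.2 set. Under the multiple imputation in SAP F.3.1, the two differ only in how missing scores are handled. In neither case is a deviating completer removed.

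**Step 3. The plan's own figure.** Inputs from Protocol 10.1 and 10.3.2: two-sided alpha 0.05, power 0.9, SD 29.85 mm, difference 11 mm. Reading 29.85 as the SD of the paired differences:

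N = (1.960 + 1.282)² × 29.85² / 11² = 77.4, so 78 in total, or 39 per sequence.

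39 / 0.93 = 41.9, so 42 per sequence and 84 in total. Both match the protocol. The planned standard error is 29.85 / √78 = 3.38 mm.

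**Step 4. Illustration of size.** Assumptions, none from the documents: 78 completers, an effect of 11 mm in compliers, and k deviators balanced across sequences with mean effect d. The estimate with everyone in is 11 − (k/78)(11 − d). Removing the deviators moves it by

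shift = (k/78) × (11 − d).

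| k | d = 11 | d = 5.5 | d = 0 |
|---|---|---|---|
| 4 (5%) | 0 mm | 0.28 mm | 0.56 mm |
| 8 (10%) | 0 mm | 0.56 mm | 1.13 mm |

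The largest entry is 1.13 / 3.38 = 0.33 of a standard error and 1.13 / 11 = 10% of the 11 mm difference. F.1.2 removes none of these participants, so the shift would not be seen.

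**Step 5. Precision lost by applying the protocol's rule.** With 74 participants the standard error is 29.85 / √74 = 3.47 mm; with 70 it is 29.85 / √70 = 3.57 mm.

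**The case against.** The conflict with Protocol 10.7 is plain on the text. The best case for the SAP concerns what surrounds it.

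- **F.1.2 can be read together with E.4.7.** Its conditional opening may refer back to E.4.7, so that having both procedures is an added requirement on top of compliance, or is the SAP's working definition of compliance. This softens the conflict inside the SAP, because compliance is undefined. It does not account for the sentence that keeps completers whose sequence differs from allocation, and it does not restore the missing deviation test to F.1.2.
- **Few deviations are likely.** Visits are booked at least 4 weeks apart (Protocol 10.8). A missed second visit is rearranged within that limit or the participant counts as lost to follow-up (7.6). Eligibility is checked against a list (7.1.2), and planned deviations are barred (12.5). This stands: cases should be uncommon, though accidental ones remain possible.
- **A wrong-order completer may do no harm.** Such a participant supplies both scores, and analysis by the order received keeps the period labels right. This stands as an argument about bias. It is not a reason to leave their place in the set unstated.
- **The illustration is weak.** With d = 0, the shift as a share of 11 mm is simply k/78, so the 10% restates the assumed deviation rate. Nor is the grid a bound, since deviators could have a reversed or larger effect. Both points stand; the figures show scale only.
- **The analysis is of low rank.** Protocol 10.3.2 says: "The secondary analyses should be considered as hypothesis generating rather than providing firm conclusions". This stands and limits the severity.

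**Conclusion.** The concern holds. F.1.2 as written gives a per-protocol set that differs from the one in Protocol 10.7 and has no counterpart to the compliance restriction in Protocol 10.3.2 and SAP E.4.7. The mismatch with Protocol 10.7 is certain. The mismatch with the compliance wording is less exact, because that term is undefined.

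The consequence is that the only planned check on deviations checks nothing beyond non-completion. On the assumptions above, the movement that would go unseen ranges from 0 to 1.1 mm against a standard error of 3.4 mm. The true figure depends on a deviation rate and an effect in deviators that the documents do not give. The primary test and the sample size are untouched. This should be corrected before database lock, but it does not threaten the trial's main conclusion.

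**What to change.** 1. Replace the rule in SAP F.1.2 with the Protocol 10.7 criterion: no major protocol deviation, and completion as originally allocated.
2. State whether a completer treated in the wrong order is excluded. Since Protocol 7.3 allocates only the order, exclusion is the natural reading; on that reading, delete the sentence on sequence received from the per-protocol definition.
3. List the major deviations before database lock, saying for each of an eligibility breach and an interval below the protocol's minimum whether it counts. Use the same list to define compliance in E.4.7.
4. Give the completers rule, by sequence received, its own entry for the other secondary analyses.
5. While editing, correct the cross-references: E.5.4 should point to E.4.6, and E.5.5 to E.4.7 (there is no E.4.8). E.5.3 reads "preference for each impression (Section E.4.6) will be tabulated and reported using frequencies and percentages", but E.4 has no entry for operator preference, and G.1.2 places that outcome outside the SAP; those two need reconciling. This item is clerical and does not affect membership of the set.

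The cost is SAP wording. No new data are needed: treatment dates are on the CRF (Protocol 9.1), and non-compliances go in the CRF or a log (12.5). The per-protocol set may be slightly smaller, with the modest loss of precision shown in step 5 of the working.
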